#### 7.5.3.2 Clinically notable below normal values

- Systolic BP:  $\leq 90$  mmHg and a decrease  $\geq 20$  mmHg from baseline
- Diastolic BP:  $\leq 50$  mmHg and a decrease  $\geq 15$  mmHg from baseline
- Supine pulse:  $\leq 50$  bpm with decrease from baseline  $\geq 15$  bpm

### 7.5.4 ECG

Bazett's formula (QTcB) and Fridericia's formula (QTcF) will be used to calculate the heart rate-corrected QT interval (msec) on the heart rate (HR bpm) and QT (msec) as follows.

$QTcB$  (msec) =  $QT / (RR)^{1/2}$  and  $QTcF$  (msec) =  $QT / (RR)^{1/3}$  All ECG data (heart rate (bpm), PR interval (msec), QT interval (msec), QRS duration (msec), QTcB interval (msec)) will be listed by patient and visit/time. Abnormalities will be flagged.

Summary statistics (n, mean, standard deviation, minimum, median, and maximum) will be provided by visit/time for the above parameters. Descriptive statistics will be provided for change from baseline to different time points in heart rate, PR interval, QT interval, QRS duration, and QTcB interval. Shift table based on notable values will be provided for ECGs.

The notable criteria for PR is

- Increase  $> 25\%$  compared to baseline to a post-baseline value  $> 200$  ms

The notable criteria for QRS is

[figure not shown]
- Increase  $> 25\%$  compared to baseline to a post-baseline value  $> 110$  ms

The notable criteria for HR are

- Increase > 25% compared to baseline to a post-baseline value > 100 bpm
- Decrease > 25% compared to baseline to a post-baseline value < 50 bpm

The notable criteria for QT, QTcF, and QTcB are

- an increase from baseline > 30 ms at any post-baseline
- an increase from baseline > 60 ms at any post-baseline

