20. Patients with a history of non-compliance to medical regimens or who are considered potentially unreliable or will be unable to complete the entire study.
21. Patients who have received pituitary irradiation within five years prior to Visit 1.
22. Patients with risk factors for QTc prolongation or Torsade de Pointes, i.e. patients with a baseline QTcF > 470ms, hypokalemia, hyperkalemia, hypocalcaemia, hypomagnesaemia, uncontrolled hypothyroidism, personal or family history of long QT syndrome, or concomitant medications known to prolong the QT interval.

[figure not shown]
No additional exclusions may be applied by the investigator, in order to ensure that the study population will be representative of all eligible patients.

5 Treatment

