5.5.11 Discontinuation of study treatment

Patients may voluntarily discontinue from the study treatment for any reason at any time. If a patient decides to discontinue from the study treatment, the investigator should make a reasonable effort (e.g. telephone, email, letter) to determine the primary reason for this decision and record this information in the patient's chart and on the appropriate CRF pages. They may be considered withdrawn if they state an intention to withdraw, fail to return for visits, or become lost to follow-up for any other reason.

The investigator should discontinue study treatment for a given patient if he/she believes that continuation would be detrimental to the patient's well-being.

Study treatment must be discontinued under the following circumstances and according to Investigator discretion:

- Withdrawal of informed consent.
- Emergence of the following adverse events (compound specific):
 - hypertension defined as office mean sitting systolic BP > 180 mmHg or mean sitting diastolic BP > 110 mmHg (confirmed and persistent*).
- Any of the following laboratory abnormalities:
 - hyperkalemia (serum potassium > 5.5 mmol/L; confirmed and persistent*).
 - hypokalemia (serum potassium < 3.5 mmol/L; confirmed and persistent*).
 - hyponatremia (serum sodium < 130 mmol/L; confirmed and persistent*).
- QTcF > 500 msec, if confirmed by a cardiologist (see [Section 6.6.5](#)).
- QTcF > 480 msec, if the investigator determines it is no longer safe for the patient to continue in the study, based on ECGs, cardiac examination, and recommendation from a cardiologist (see [Section 6.6.5](#)).
- Pregnancy.
- Use of any other therapy for Cushing's disease.
- Any other protocol deviation that results in a significant risk to the patient's safety.

* Persistent is defined as unresolved with LCI699 dose or other concomitant medication changes

Patients who discontinue study treatment should NOT be considered withdrawn from the study. They should return for the assessments indicated in [Section 6](#). If they fail to return to return for these assessments for unknown reasons, reasonable effort (e.g. telephone, email, letter) should be made to contact them as specified in [Section 5.5.13](#).

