6.6.5 Electrocardiogram (ECG)

Cardiac monitoring will include 12-lead Safety ECGs, which are the primary assessment of safety at study visits, and 24-hour continuous 12-lead Holter recordings, which provide large amounts of additional ECG data with central reading, but are not intended to provide real-time assessment of cardiac intervals and cardiac rhythm.

Twenty-four hour continuous 12-lead Holter recording with central reading of data are done on each patient according to the [Assessment schedules](#).

Twelve-lead safety ECGs are collected at the study sites according to the [Assessment schedules](#). At each visit when a study drug dose is administered, the safety ECG should be collected at 1.5 hours post-dose (approximately at the time of C_{max}). If the patient chooses to enroll in long term extension-1 and long term extension-2 studies, 12-lead safety ECGs will also be done according to the [Assessment schedules](#), and the timing will also be 1.5 hours post-dose if study drug is administered.

Twelve-lead safety ECGs are collected at the study site using local ECG equipment. This ECG must be read on site by a qualified physician (e.g., the investigator, or another qualified physician such as a consulting cardiologist) at the time they are collected and documented on the ECG section of the CRF / eCRF.

Each 12-lead Safety ECG tracing should be labeled with the:

- study number
- patient initials
- patient number
- date and time

and kept in the source documents at the study site. The clock on the ECG machine should be synchronized with the central clock on a daily basis.

The eCRF will contain:

- date and time of ECG
- heart rate
- PR interval
- QT and QTc interval

- QRS duration

The Fridericia QT formula (QTcF) to correct for variations in heart rate should be used for clinical decisions ([Fridericia 1920](#)).

The purpose of the safety ECG is to identify patients with clinically significant (“notable”) ECG abnormalities. On the day of the first study drug administration (day 1), the pre-dose ECG must be done in triplicate. The mean of the QTcF from these 3 tracings is used as the baseline QTcF to be compared with the 1.5 hour post-dose ECG on Day 1 only.

Only ECGs with clinically significant (“notable”) abnormalities should be reported on the ECG tracing. A “notable abnormality” is defined as:

- Day 1 only: an increase in QTcF > 30msec at 1.5 hours post-dose, compared to the mean pre-dose baseline QTcF from the same day

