- QTcF > 480msec with acute cardiovascular risk, as assessed by a consulting cardiologist
- Any QTcF > 500msec, confirmed by a consulting cardiologist

Notable ECG abnormalities should be recorded on the Adverse Events e(CRF) page. The overall interpretation will be collected with a Yes/No statement to confirm if any clinically significant abnormalities are present which need to be specified further.

For any ECGs with patient safety concerns, two additional 12-lead ECGs should be performed to confirm the safety finding. If there is a notable abnormality, then a cardiology consult should be called, and the Novartis Medical Monitor for this trial notified of the event.

ECGs must be recorded after 10 minutes rest in the supine position to ensure a stable baseline. The preferred sequence of cardiovascular data collection during study visits is ECG collection first, followed by vital signs, and then blood sampling for LCI699 pharmacokinetic (PK) assessment ([Figure 6-1](#)).

Figure 6-1 Sequence of cardiovascular data collection

Original ECG tracings, appropriately signed, will be archived at study site.

QT prolongation monitoring

On the day of the first administration of LCI699 (day 1), the pre-dose baseline ECG must be done in triplicate. The mean of the QTcF values from these three ECG tracings is used to determine the mean baseline QTcF for that day only. If the safety ECG (1.5 hours post-first dose of LCI) shows an increase in QTcF > 30ms from the mean baseline value, or the QTcF is > 480ms, then the patient should be discontinued from study drug. Any ECG in doubt

should be reviewed promptly by a consulting cardiologist before discontinuing the patient from LCI699 therapy.

If at any follow up visit, a QTcF > 500msec is observed on the 1.5 hour post-dose safety ECG, then triplicate ECGs, each 2-3 minutes apart, need to be taken after the initial ECG. The mean QTcF from the triplicate ECGs will be determined. If the mean QTcF is > 500msec, the patient has to interrupt study treatment while an urgent cardiology consultation is obtained to re-evaluate the ECG and perform a clinical consultation. If immediate treatment is required for patient safety, this should be initiated at the study site without delay and without waiting for confirmation by a cardiologist.

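### SAP 7.5.4 derives QTcF but names only QTcB in the ECG listing and change-from-baseline statistics, and SAP 8.2 leaves open whether the Day 1 pre-dose ECG is baseline

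*SAP*

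**What the plan says.** SAP 7.5.4 gives formulas for both Bazett (QTcB) and Fridericia (QTcF). What it then reports is as follows.

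- Listing: heart rate, PR, QT and, to close the list, "QRS duration (msec), QTcB interval (msec)) will be listed by patient and visit/time".
- By-visit summaries (n, mean, SD, minimum, median, maximum): the parameters just named, by back-reference.
- Change from baseline: "change from baseline to different time points in heart rate, PR interval, QT interval, QRS duration, and QTcB interval".
- Notable values: "The notable criteria for QT, QTcF, and QTcB are" rises from baseline above 30 ms and above 60 ms at any post-baseline time. These feed a shift table.

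The protocol runs on QTcF. Section 6.6.5 states: "The Fridericia QT formula (QTcF) to correct for variations in heart rate should be used for clinical decisions". Section 4.2 excludes "patients with a baseline QTcF > 470ms". Section 5.5.11 lists "QTcF > 500 msec, if confirmed by a cardiologist" among the discontinuation criteria. The notable abnormalities in 6.6.5 include "QTcF > 480msec with acute cardiovascular risk, as assessed by a consulting cardiologist", and "Notable ECG abnormalities should be recorded on the Adverse Events e(CRF) page".

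On baseline, SAP 8.2 uses the last available ECG taken before dosing and before study Day 1. SAP 8.1 defines Day 1 as the date of first dose. SAP 8.2 adds that, among several measurements on one day, the last one before dose is used. Protocol 6.6.5 requires a triplicate pre-dose ECG on Day 1 and averages it, for comparison with the post-dose ECG of that day only. Protocol 3.1, describing interim escalation visits, measures a QTcF rise above 60 ms from the Day 1 pre-dose ECG.

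**The concern.** The Final CSR is meant to concentrate on long-term safety and efficacy (SAP 3), and SAP 7.5 names ECG data as part of the safety assessment. SAP 1 itself records that the maximum dose was lowered in Amendment 5 because of QTcF. A reader of that report would expect QTcF by visit. As the text stands, the reader gets QTcB by visit and, for QTcF, only a categorical table of rises.

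That table depends on the baseline. If two programmers can choose different baseline ECGs from SAP 8.2, they can fill the only named QTcF output differently.

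The protocol's other QTcF analysis, the exposure-response work in 9.5.8, does not fill the gap in this report. SAP 7.4 puts no PK analyses in the Final CSR, and the PK/PD row of SAP Table 6-1 has no analysis set marked.

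**Working it through.** The plan states no figure here to reproduce. The check sets the passages side by side, with one illustration.

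**1. Which outputs name QTcF**

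| SAP 7.5.4 output | Heart rate, PR, QT, QRS | QTcB | QTcF |
|---|---|---|---|
| Listing | named | named | not named |
| By-visit summaries (6 statistics) | by back-reference | by back-reference | not covered on the natural reading |
| Change from baseline | named | named | not named |
| Criteria for rises >30 / >60 ms, shift table | QT only, of these four | named | named |

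QTcF is 0 of the 5 parameters in the listing and 0 of the 5 in the change-from-baseline sentence. The latter is a closed list.

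**2. Which QTcF values could escape every table**

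The SAP's QTc criteria are increases only. Combine them with the protocol's limits:

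- To exceed 480 ms with a rise of no more than 30 ms, baseline must be above 480 − 30 = 450 ms.
- Eligibility allows a baseline up to 470 ms, so baselines above 450 and up to 470 ms qualify.
- From 470 ms, a rise of 30 ms reaches 470 + 30 = 500 ms.

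So an eligible patient can have a follow-up QTcF above 480 and up to 500 ms without meeting the >30 ms criterion. If there is also no acute cardiovascular risk, the >480 ms criterion in protocol 6.6.5 is not met, and that section does not send the ECG to the AE page. Such a value need not appear in any table. A value above 500 ms from a baseline of 470 ms or less is a rise of more than 30 ms and does reach the shift table, but there it is not separated from a rise of the same category at a much lower level. This step assumes that the SAP baseline also satisfies the 470 ms limit.

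**3. Can QTcB stand in for QTcF? (illustration only)**

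With QTcB = QT/RR^(1/2), QTcF = QT/RR^(1/3) and RR = 60/HR:

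QTcB = QTcF × (HR/60)^(1/6)

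At constant QTcF, the shift in QTcB is QTcF × [(HR2/60)^(1/6) − (HR1/60)^(1/6)]. Assumed values, not from the documents: QTcF 380 to 410 ms, starting rate 70 bpm.

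| Rate change | Shift in QTcB at constant QTcF |
|---|---|
| 0 | 0 ms |
| +5 bpm | 4.5 to 4.9 ms |
| +10 bpm | 8.8 to 9.5 ms |
| −10 bpm | −9.9 to −10.7 ms |

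In the other direction, if QTcF rises by 35 ms (420 to 455) while heart rate falls from 80 to 65 bpm, QTcB rises by only 20.5 ms. The two measures agree when heart rate is stable and separate when it is not. The documents report no heart-rate change, so this shows only that one table cannot be assumed to replace the other.

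**4. Which ECG is baseline**

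- Literal reading: Day 1 is the first-dose date, baseline lies before Day 1, so the Day 1 pre-dose ECG is out. The assessment schedule has a safety ECG at the baseline visit, and that would be used.
- Other reading: if baseline must lie before Day 1 anyway, the added condition that it be taken before dosing does no work. The rule choosing the last same-day reading before dose also makes most sense if Day 1 readings can count. The schedule has a safety ECG on Day 1 as well.
- Protocol 3.1 uses the Day 1 pre-dose ECG for its 60 ms rise. Protocol 6.6.5 lists no 60 ms criterion and confines the triplicate mean to Day 1.
- If Day 1 counts, SAP 8.2 takes the last of the three tracings, while protocol 6.6.5 takes their mean.

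**The case against.** The best reply is that this is an incomplete parameter list and not a decision. Section 7.5.4 opens with all ECG data and with the QTcF formula, so the back-reference in the summary sentence could be stretched to QTcF. Protocol 9.5.3 asks only for listing, flagging and summary statistics, and names no correction. QTcF also remains in the shift table, and it can be recalculated by hand from the listed QT and heart rate. Most of this stands. A reader might infer that the SAP abandons QTcF or breaches 9.5.3; neither is so. The mismatch is with the protocol's QTcF-based rules. What the reply does not repair is the closed change-from-baseline list.

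On the absolute limits, a reader might infer that every QTcF between 480 and 500 ms would vanish from the report. It would not. Under protocol 6.6.5, a QTcF above 480 ms after the first dose leads to discontinuation, which the disposition summary (SAP 7.1.2) counts. Cardiologist-confirmed values above 500 ms go to the AE page, and rises above 30 ms reach the shift table. The gap is the narrow follow-up case in step 2. The AE groupings in SAP 7.5.1.4 sit in an external file, so what they would add is unknown.

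On baseline, SAP Table 8-1 labels Visit 2 as baseline and Day 1 as treatment, which favours the literal reading. SAP 8.2 already has a last-available rule and a same-day rule. So a reader who concludes that patients without a Day 1 ECG or triplicate have no baseline goes too far. The triplicate mean is confined to the Day 1 comparison, so its difference from the SAP rule is a matter for reconciliation and not a contradiction in itself. What remains is whether the Day 1 pre-dose ECG counts.

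**Conclusion.** The point holds as a reporting defect that should be corrected. The text of SAP 7.5.4 yields no QTcF descriptive statistics by visit and no QTcF change from baseline. That rests on reading the summary sentence as referring to the five listed parameters; the change-from-baseline gap needs no such reading. The missing counts at 480 and 500 ms leave one narrow class of follow-up values outside the tables. The baseline wording is ambiguous on a single question, and protocol 3.1 conflicts with its literal reading.

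The stronger inference, that QT prolongation would be concealed or that the safety results are biased, has no support. The documents show no heart-rate change and no missed signal, and protocol 3.5 reports that the thorough QT study predicted a mean effect below the threshold of regulatory concern. The QTcB shifts above rest on assumed values and measure no effect in this trial. No efficacy result is touched.

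**What to change.** - **SAP 7.5.4:** add QTcF to the listing, the by-visit summaries and the change-from-baseline statistics, and keep QTcB.
- **SAP 7.5.4:** tabulate the number of patients with post-baseline QTcF above 480 ms and above 500 ms, the limits already in the protocol.
- **SAP 8.2:** state whether a Day 1 pre-dose ECG counts as baseline. Keep the existing last-available rule for patients without one.
- **SAP 8.2 with protocol 3.1 and 6.6.5:** reconcile the last-reading rule with the triplicate mean, and reconcile the passages on which baseline a QTcF rise is measured from.

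The cost is SAP wording and minor programming. QTcF and its change from baseline must already be derived for the >30 and >60 ms criteria, and the eCRF holds heart rate and QT, so no new data are needed.

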If the cardiologist confirms a mean QTcF > 500msec, the patient has to discontinue according to the discontinuation procedure described in [Section 5.5.9](#). The patient must remain under observation until the QTcF is < 480msec and serum electrolytes, calcium, and magnesium are measured and the results normal. This observation may be done at the site, in an Emergency Room, or a cardiology clinic, as appropriate and depending upon local resources.

Otherwise, and if the cardiologist confirms, that at least one ECG shows a QTcF > 480msec, the cardiac assessments described for a confirmed QTcF > 480msec need to be followed.

[figure not shown]
If at any follow up visit a $480\text{msec} < \text{QTcF} \leq 500\text{msec}$ is observed on the 1.5 hour post-dose safety ECG, the following steps need to be taken (described in [Figure 6-2](#)):

The patient has to interrupt study treatment while an urgent cardiology consultation is obtained to re-evaluate the ECG. If immediate treatment is required for patient safety this should be initiated at the study site without delay and without waiting for confirmation by a cardiologist.

- If a QTcF > 480msec is NOT confirmed, no further action needs to be taken;
- If a QTcF > 480msec is confirmed, a cardiologist must perform a thorough clinical evaluation to assess the patient for acute cardiovascular risk, and for possible underlying heart disease that needs additional evaluation and management.
 - a. If based upon the assessment by the cardiologist, the investigator considers that there is an acute cardiovascular safety risk and that the subject should not continue with study medication, the subject needs to be discontinued immediately (discontinuation criteria described in [Section 5.5.9](#)).
 - b. If based upon the assessment by the cardiologist, the investigator considers that there is not an acute cardiovascular safety risk, the subject can continue to receive study medication.

The patient must remain under observation until the QTcF is < 480msec and serum electrolytes, calcium, and magnesium are measured and the results are normal. This observation may be done at the site, in an Emergency Room, or a cardiology clinic, as appropriate and depending upon local resources. The results of the ECGs, cardiac examination and the recommendation by the cardiologist must be evaluated by the investigator to determine whether the subject should continue in the trial or not.

Figure 6-2 QT Prolongation Monitoring Flow Chart

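### SAP 7.5.4 defines notable QTcF only by rise from baseline, so a value of 481–500 ms that triggers interruption under the protocol can carry no notable finding, and values above 500 ms have no category of their own

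*SAP*

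**What the plan says.** **SAP 7.5.4 (ECG).** Two notable criteria apply to QT, QTcF and QTcB alike: "an increase from baseline > 30 ms at any post-baseline" and "an increase from baseline > 60 ms at any post-baseline". In the same section, PR, QRS and heart rate each need a change of more than 25% together with an absolute value (PR above 200 ms, QRS above 110 ms, heart rate above 100 or below 50 bpm). The output that uses these criteria is described as follows: "Shift table based on notable values will be provided for ECGs". The listing is specified as "QRS duration (msec), QTcB interval (msec)) will be listed by patient and visit/time". It names QTcB but not QTcF, as do the change-from-baseline summaries. Abnormalities are to be flagged in the listing, with no QTc limit given other than the two rises.

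**Protocol 4.2, exclusion 22.** Among those excluded are "patients with a baseline QTcF > 470ms", so the entry cap is 470 ms.

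**Protocol 6.6.5 and 5.5.11.** QTcF is the correction used for clinical decisions.
- Above 480 and up to 500 ms at follow-up, drug is interrupted while an urgent cardiology opinion is sought. "If a QTcF > 480msec is confirmed, a cardiologist must perform a thorough clinical evaluation".
- If the mean of repeat ECGs exceeds 500 ms, drug is also interrupted. The discontinuation list includes "QTcF > 500 msec, if confirmed by a cardiologist".
- ECGs defined as notable go to the adverse event page. That covers confirmed values above 500 ms, values above 480 ms with acute cardiovascular risk and, on Day 1 only, a rise above 30 ms.

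**Protocol 3.1.** At the interim escalation visits, a rise above 60 ms is notable as well, alongside the 480 and 500 ms limits.

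**The concern.** The protocol's notable definitions combine rises (30 and 60 ms) with absolute limits (480 and 500 ms). The SAP uses the same two rise figures and neither absolute limit. QT is also the only ECG parameter in SAP 7.5.4 without an absolute component.

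A rise-only rule has two consequences. It can miss a patient who starts high and crosses 480 ms on a small rise. It also gives the same class to patients whose final values mean quite different things under the protocol.

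Amendment 5 intensified ECG monitoring and lowered the maximum dose because of QT prolongation. The Final CSR covers safety over the whole study, so it should be able to say how many patients crossed the limits the protocol acts on, even if the answer is none.

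**Working it through.** The plan states no figure to reproduce here. The check is threshold arithmetic.

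**Inputs**
- SAP classes by rise d = v − b, where b is baseline and v is the post-baseline QTcF: none if d ≤ 30; above 30 if 30 < d ≤ 60; above 60 if d > 60 (SAP 7.5.4).
- b ≤ 470 ms (Protocol 4.2, exclusion 22).
- Limits acted on at follow-up: 480 and 500 ms (Protocol 6.6.5, 5.5.11).

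**Step 1: can a value above 480 ms go unflagged?** It must satisfy v > 480 and v − b ≤ 30, so b ≥ v − 30 > 480 − 30 = 450. With b ≤ 470, the highest unflagged value is 470 + 30 = 500. Baselines above 450 and up to 470 ms can therefore give values above 480 and up to 500 ms with no notable finding. In whole milliseconds, these are baselines 451 to 470 and values 481 to 500.

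**Step 2: can a value above 500 ms go unflagged?** With b ≤ 470 and v > 500, d > 500 − 470 = 30. It always meets the 30 ms criterion. For v = 501, the 60 ms criterion needs b < 501 − 60 = 441. Baselines of 440 or less fall in the above-60 class, and baselines 441 to 470 fall only in the above-30 class.

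**Step 3: SAP class for selected pairs (ms)**

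| Baseline | 481 | 485 | 490 | 500 | 501 | 531 |
|---|---|---|---|---|---|---|
| 450 | >30 | >30 | >30 | >30 | >30 | >60 |
| 451 | none | >30 | >30 | >30 | >30 | >60 |
| 455 | none | none | >30 | >30 | >30 | >60 |
| 460 | none | none | none | >30 | >30 | >60 |
| 470 | none | none | none | none | >30 | >60 |
| 471 | none | none | none | none | none | >30 |

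Each entry of none in the columns 481 to 500 is a value that requires interruption pending review at follow-up.

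**Step 4: loss of distinction.** 501 − 470 = 31 and 411 − 380 = 31. Both fall in the above-30 class, although only the first exceeds 500 ms.

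**Step 5: sensitivity to the baseline.** SAP 8.2 takes the last ECG before Day 1 as baseline. The last row of the table applies only if that ECG exceeds 470 ms, for example through an entry deviation. Then 471 to 501 ms is a rise of 30 ms, and a value above 500 ms also escapes.

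**Step 6: does the adverse event page close the gap?** Under Protocol 6.6.5, a value above 480 and up to 500 ms is notable only with acute cardiovascular risk. A confirmed 490 ms without such risk, from a baseline of 460 ms (+30), interrupts drug but is notable under neither document. Protocol 7.1 still lets an investigator report it as clinically significant, but that is a judgement and not a rule.

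**The case against.** The case against has real force on several points.

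- **Above 500 ms.** A reader might infer that values above 500 ms go uncounted. The documents do not support that. Under the 470 ms cap every such value is a rise above 30 ms. Confirmed cases also go to the adverse event page, and adverse events are tabulated. They meet a discontinuation criterion too, and SAP 7.1.2 summarises reasons for discontinuation. What is missing is a separate category.
- **The protocol uses rises too.** A reader might infer that the protocol works on absolute QTcF alone. It does not: 30 ms on Day 1 and 60 ms at interim visits match the SAP's figures. The gap is that the SAP stops there.
- **No commitment is broken.** Protocol 9.5.3 promises listings with flags and summaries by visit, not an outlier table.
- **The listing could show the values.** With about 19 patients, individual readings can be inspected. This stands only in part. As written, the listing names QTcB, and its flags have no stated absolute QTc limit. Even with QTcF added, a maximum by visit does not count patients.
- **The risk has been reassessed.** Protocol 3.5 reports that the thorough QT study predicted a mean effect below regulatory concern for 2–30 mg bid. That lowers the stakes. A mean effect does not say whether individuals crossed a limit, and the protocol kept its limits.
- **Interruption at 480–500 ms is provisional.** If the cardiologist does not confirm the value, no further action follows, so a raw count would exceed the confirmed count. This stands and belongs in a footnote to the table.

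**Conclusion.** The point holds in a limited form. The uncounted region is QTcF above 480 and up to 500 ms in patients with baseline above 450 and up to 470 ms. Within it, values without acute cardiovascular risk also fall outside the protocol's rule for notable ECGs on the adverse event page. Above 500 ms the shortfall is one of presentation, provided the SAP baseline respects the 470 ms cap.

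The documents give no distribution of baseline QTcF for these cohorts, so the number affected cannot be estimated and may be zero. With 19 patients enrolled under Amendment 4, one missed patient would be 1/19, about 5%.

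This is a minor reporting improvement, not a departure from the protocol, and it does not question any of the clinical limits.

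**What to change.** In SAP 7.5.4 add, for QTcF, the number and percentage of patients with a new post-baseline value above 480 ms and above 500 ms, shown alongside the rise classes above 30 and above 60 ms. These are the protocol's own limits, used only for counting. Flag the same values in the by-patient listing and name QTcF there, so that the flag has a column to sit in. Add a footnote that the counts rest on recorded values and include readings above 480 ms that the cardiologist did not confirm.

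An absolute class also gives the planned shift table a baseline category to shift from, which a rise cannot.

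The cost is one extra table and a listing flag. The eCRF already holds heart rate and QT, and SAP 7.5.4 already gives the QTcF formula, so no new data are needed.
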